**Appendix 5 ECOG Performance Status**

0	Fully active, able to carry on all pre-disease performance without restriction
1	Restricted in physically strenuous activity but ambulatory and able to carry out work of a light or sedentary nature, e.g., light house work, office work
2	Ambulatory and capable of all selfcare but unable to carry out any work activities. Up and about more than 50% of waking hours.
3	Capable of only limited selfcare, confined to bed or chair more than 50% of waking hours.
4	Completely disabled. Cannot carry on any selfcare. Totally confined to bed or chair.
5	Dead

## Appendix 6 NYHA Functional Classification

NYHA Class	Symptom
I	No symptoms and no limitation in ordinary physical activity, e.g. shortness of breath when walking, climbing stairs etc.
II	Mild symptoms (mild shortness of breath and/or angina) and slight limitation during ordinary activity.
III	Marked limitation in activity due to symptoms, even during less-than-ordinary activity, e.g. walking short distances (20–100 m). Comfortable only at rest.
IV	Severe limitations. Experiences symptoms even while at rest . Mostly bedbound patients.

## Appendix 7 SF-36

SF-36v2® Health Survey © 1992, 1996, 2000 Medical Outcomes Trust and QualityMetric Incorporated. All rights reserved.

SF-36® is a registered trademark of Medical Outcomes Trust.  
(SF-36v2® Health Survey Standard, United States (English))

### Your Health and Well-Being

**This survey asks for your views about your health. This information will help keep track of how you feel and how well you are able to do your usual activities. *Thank you for completing this survey!***

**For each of the following questions, please mark an  in the one box that best describes your answer.**

**1. In general, would you say your health is:**

Excellent	Very good	Good	Fair	Poor
.	.	.	.	.
 1	 2	 3	 4	 5

**2. Compared to one year ago, how would you rate your health in general now?**

Much better now than one year ago	Somewhat better now than one year ago	About the same as one year ago	Somewhat worse now than one year ago	Much worse now than one year ago
.	.	.	.	.
 1	 2	 3	 4	 5

3. The following questions are about activities you might do during a typical day. Does your health now limit you in these activities? If so, how much?

	Yes, limited a lot	Yes, limited a little	No, not limited at all
	.	.	.

- a Vigorous activities, such as running, lifting heavy objects, participating in strenuous sports.....  1.....  2 .....  3
- b Moderate activities, such as moving a table, pushing a vacuum cleaner, bowling, or playing golf .....  1.....  2 .....  3
- c Lifting or carrying groceries.....  1.....  2 .....  3
- d Climbing several flights of stairs.....  1.....  2 .....  3
- e Climbing one flight of stairs.....  1.....  2 .....  3
- f Bending, kneeling, or stooping.....  1.....  2 .....  3
- g Walking more than a mile .....  1.....  2 .....  3
- h Walking several hundred yards.....  1.....  2 .....  3
- i Walking one hundred yards .....  1.....  2 .....  3
- j Bathing or dressing yourself .....  1.....  2 .....  3

4. During the past 4 weeks, how much of the time have you had any of the following problems with your work or other regular daily activities as a result of your physical health?

	All of the time	Most of the time	Some of the time	A little of the time	None of the time
	.	.	.	.	.

- a Cut down on the amount of time you spent on work or other activities .....  1 .....  2 .....  3 .....  4 .....  5
- b Accomplished less than you would like.....  1 .....  2 .....  3 .....  4 .....  5
- c Were limited in the kind of work or other activities.....  1 .....  2 .....  3 .....  4 .....  5
- d Had difficulty performing the work or other activities (for example, it took extra effort) .....  1 .....  2 .....  3 .....  4 .....  5

5. During the past 4 weeks, how much of the time have you had any of the following problems with your work or other regular daily activities as a result of any emotional problems (such as feeling depressed or anxious)?

	All of the time	Most of the time	Some of the time	A little of the time	None of the time
	.	.	.	.	.

- a Cut down on the amount of time you spent on work or other activities .....  1 .....  2 .....  3 .....  4 .....  5
- b Accomplished less than you would like.....  1 .....  2 .....  3 .....  4 .....  5
- c Did work or other activities less carefully than usual .....  1 .....  2 .....  3 .....  4 .....  5

6. During the past 4 weeks, to what extent has your physical health or emotional problems interfered with your normal social activities with family, friends, neighbors, or groups?

	Not at all	Slightly	Moderately	Quite a bit	Extremely
	.	.	.	.	.

 1	 2	 3	 4	 5
----------------------------	----------------------------	----------------------------	----------------------------	----------------------------

7. How much bodily pain have you had during the past 4 weeks?

None	Very mild	Mild	Moderate	Severe	Very severe
 1	 2	 3	 4	 5	 6

8. During the past 4 weeks, how much did pain interfere with your normal work (including both work outside the home and housework)?

Not at all	A little bit	Moderately	Quite a bit	Extremely
 1	 2	 3	 4	 5

9. These questions are about how you feel and how things have been with you during the past 4 weeks. For each question, please give the one answer that comes closest to the way you have been feeling. How much of the time during the past 4 weeks...

All of the time	Most of the time	Some of the time	A little of the time	None of the time
-----------------	------------------	------------------	----------------------	------------------

a Did you feel full of life? .....  1 .....  2 .....  3 .....  4 .....  5b Have you been very nervous? .....  1 .....  2 .....  3 .....  4 .....  5c Have you felt so down in the dumps that nothing could cheer you up? .....  1 .....  2 .....  3 .....  4 .....  5d Have you felt calm and peaceful? .....  1 .....  2 .....  3 .....  4 .....  5e Did you have a lot of energy? .....  1 .....  2 .....  3 .....  4 .....  5f Have you felt downhearted and depressed? .....  1 .....  2 .....  3 .....  4 .....  5g Did you feel worn out? .....  1 .....  2 .....  3 .....  4 .....  5h Have you been happy? .....  1 .....  2 .....  3 .....  4 .....  5i Did you feel tired? .....  1 .....  2 .....  3 .....  4 .....  5

10. During the past 4 weeks, how much of the time has your physical health or emotional problems interfered with your social activities (like visiting with friends, relatives, etc.)?

All of the time	Most of the time	Some of the time	A little of the time	None of the time
 1	 2	 3	 4	 5

11. How **TRUE** or **FALSE** is each of the following statements for you?

Definitely true	Mostly true	Don't know	Mostly false	Definitely false
-----------------	-------------	------------	--------------	------------------

- a I seem to get sick a little easier than other people .....  1 .....  2 .....  3 .....  4 .....  5
- b I am as healthy as anybody I know.....  1 .....  2 .....  3 .....  4 .....  5
- c I expect my health to get worse.....  1 .....  2 .....  3 .....  4 .....  5
- d My health is excellent .....  1 .....  2 .....  3 .....  4 .....  5

*Thank you for completing these questions!*

## Appendix 8 Renal Scoring

### Approach to scoring amyloid and chronic lesions in kidney biopsies

Renal biopsy reports and renal biopsy slides are reviewed from patients with diagnosis of AL amyloid, based on Congo red positive, clonal staining of deposits with, where electron microscopy is available, classic randomly arranged fibrillary deposits.

For scoring of severity, a minimum of 5 glomeruli must be present. Scoring is performed on light microscopic slides. PAS and/or Jones silver stain is preferable for scoring.

Amyloid type, determined by immunofluorescence staining for kappa and lambda (or in some cases also by mass spectrometry) is noted.

#### *Scoring of biopsy adequacy and sclerosis/fibrosis lesions:*

The number of glomeruli available by light microscopy is recorded and the distribution of the biopsy, whether including cortex and/or medulla, is noted.

The percent of acute tubular injury is estimated from assessing each high-power field, giving a percentage of overall cortex involved with flattening, blebbing and/or vacuolization of tubules.

The presence of inflammation in scarred or non-scarred areas is noted.

Percent global sclerosis and segmental sclerosis is assessed.

Tubulointerstitial fibrosis is estimated, estimating degree in each high-power cortical field, to the nearest 10% with >0% and < 5% estimated as 5%, and average tubulointerstitial fibrosis calculated from all cortical fields, rounding to nearest 10%.

The sum of the percentage of global glomerulosclerosis and percentage of tubulointerstitial fibrosis generate a Composite Scarring Injury Score (CSIS) for each patient.

### *Amyloid Scoring*

The distribution of amyloid is noted, and the extent of deposition is scored on a scale of 0 to 3+ (zero, absent; 1+, minimal, 2+, moderate, and 3+, severe) for each anatomical compartment, with a single overall score based on overall involvement.

#### **Involvement of glomeruli:**

Mesangial area:

0 no glomerular amyloid

1+ up to 25% expansion of mesangial area due to amyloid deposits.

2+ involves 25-50% of the glomerular tuft.

3+ involves >50% of the glomerular tuft.

Capillary wall:

0 no capillary wall amyloid

1+ up to 25% involvement of capillary wall due to amyloid deposits.

2+ involves 25-50% of capillary wall.

3+ involves >50% of capillary wall.

**Involvement of interstitium:**

0 no amyloid in interstitium

1+ <25% of interstitial area involved with amyloid

2+ 25-50% of interstitial area involved with amyloid

3+ >50% of interstitial area involved with amyloid

**Involvement of arterioles/arteries**

Vascular lesions are scored based on overall assessment as a single score.

0 no amyloid in vessels

1+ wall thickness increased by amyloid but to a degree less than the diameter of the lumen

2+ wall thickness increased by amyloid to equal or slightly greater than the diameter of the lumen

3+ wall thickness increased by amyloid to far exceed the diameter of the lumen with extreme luminal narrowing or occlusion

The sum of mesangial, capillary, interstitial, vascular amyloid involvement generated an amyloid score (AS) for each patient.

*Other*

Additional lesions are noted. These may include other lesions related to the monoclonal protein, or other additional disease processes, such as e.g. diabetic nephropathy.

**Amyloid Renal Biopsy Scoring****Scorer:****Date:**

Biopsy Number		
Patient Identifier		
Date of Biopsy		

Number of glomeruli		
% Global sclerosis		
% Segmental sclerosis		
Sample: Cortex	Y	N
Medulla	Y	N
% ATI (to nearest 10%)		
% Tubulointerstitial fibrosis (to nearest 10%, with fibrosis present but <5% scored as 5%)		

Amyloid distribution	Distribution	0-3+	
	Mesangial		
	Capillary Wall		
	Vascular		
	Interstitial		
	Other		

Amyloid Type (specify by IF/IHC/Mass spec)	Kappa	Lambda	
---	-------	--------	--

**Other Lesions:**

LCCN	Y	N	Suspicious
LC Proximal tubulopathy	Y	N	Suspicious
Other:	Specify:		

**Inflammation:**

In scar	Y	N
In nonscar	Y	N

**Score based on:**

Report	
Slides	
Both	

## Appendix 9 Measuring GFR by [name]

### STUDY RATIONALE:

Measured GFR is the gold standard for assessing kidney function. However, measuring GFR is costly and complicated both for routine clinical use and research studies. Currently, kidney function is estimated in routine clinical practice and most research settings using estimating equations based on serum creatinine. Although serum creatinine is inexpensive, convenient, it has several limitations as it varies with age, gender and especially muscle mass and diet. Since muscle mass and diet can change with illness and its recovery, estimated GFR from serum creatinine is not very accurate or sensitive at detecting change in populations with acute or chronic illness. Novel filtration markers such as low molecular weight proteins (serum cystatin C,  $\beta$ -trace protein and  $\beta$ -2-microglobulin) and novel metabolites (accuGFR) are emerging and since they are not based on muscle mass may provide more accurate estimates especially in patients with illness. However, explicit testing is required since these markers might be influenced by inflammation and disease, as well as the treatment itself.

There is great need to accurately measure GFR for both clinical care and research studies involving new treatments. To date, there is no published data on the concordance of measured GFR and estimated GFR in patients with AL amyloidosis. The aim of this study is to assess the performance of CKD-EPI creatinine, to those using novel filtration markers in comparison to iothalamate clearance measured in AL amyloidosis patients.

### GFR measurement protocol

Non-diabetic subjects will be fasting from midnight onward on the night prior to the study visit and will be asked to avoid changes in medications that influence GFR (e.g. anti-inflammatory agents, renin angiotension blocking agents). Participants with diabetes will be asked to eat normal breakfast. All participants will be asked to drink water two to three glasses of non-caffeinated beverages at home and an additional 10 to 15 mL/kg body weight upon arrival at clinical research center).

On the day of the GFR visit, one intravenous line may be inserted. This is used for blood draws and the participant or the study nurse could elect to do repeated venipuncture to obtain the repeated blood samples. A total of 0.5 ml of iothalamate (Conray® - iothalamate meglumine injection U.S.P 60%; Mallinckrodt Inc., St. Louis, MO) will be mixed with 0.5 ml of sterile water in a syringe given subcutaneously. If an IV line is inserted, normal saline will be administered through the IV line after each blood draw to maintain patency and to assist with urine flow. Before each blood draw, a small sample of blood will be drawn and discarded before sample collection. The participant will be instructed to drink sufficient water to ensure a urine flow rate of approximately 3 mL/min to a maximum value of 10 mL/min to avoid water retention.

Table 3 and the figure below shows the timing of the urine and blood samples to be taken. The subject will be asked to void immediately prior to the iothalamate injection. The urine will be collected and this collection will be referred to as the U0 specimen. The subject will be asked to void again at approximately 1 hour after iothalamate injection. This collected urine will be referred to as Urinary Equilibrium specimen (UE). The first blood sample (P1) should be collected within 5 minutes after the void. The urinary clearance periods will begin following the P1 blood collection will consist of two timed urinary clearance periods of approximately 45 minutes (See Table 3 and Figure). For the first urine collection period, all urine voided between 60 and 105 minutes will be collected. At approximately 105 minutes, the subject will be asked to empty their bladder again. All of the urine collected between the UE and this time will be referred as the U1 sample. A second blood sample (P2) will be taken within 5 minutes after void and the second urine collection period will then begin. For the second urine collection period, all urine voided between the P2 sample (approximately 105-110 minutes) and 150 minutes will be collected. At approximately 150 minutes, the subject will be asked to empty

their bladder again. All of the urine collected between the P2 and this time will be referred as the U2 sample. Collect blood sample (P3) within 5 minutes of the void. The urine for each period (U1 and U2) will be kept in a separate container. However, all voids within a urine period can be placed in the same container (see Figure). All blood samples should be collected from the opposite arm from that which was used for the injection of iothalamate. The volume of the urine collection will be determined to the nearest mL.

**Table 3 Urine and Blood Samples for mGFR**

Minutes	-5	0	60	105	150	TOTAL (mL)
Sub-Q Injection		iothal				
Urine samples (10mL)	U0		UE	U1	U2	40
Plasma samples- (4mL).			P1	P2	P3	12
Serum sample -SST tiger top tube (10 mL)	2X					20
Snack					X	
Water			Encourage water intake			

**iothal=iothalamate**

 U1 will be collected between 60 and approximately 105 minutes. U2 will be collected between 105 and approximately 150 minutes. Urine samples will be sent to Mayo Clinic, Rochester.

 Prior to aliquot, the volume of the collection will be determined

 Plasma blood samples will be collected within 5 minutes of void.

 Plasma samples to be sent to Mayo Clinic, Rochester.

 Serum samples for assay of creatinine, urea and cystatin and optional stored samples, to be sent to University of Minnesota.

**Figure: Schematic of timing of blood and urine collections**

U0	Baseline	Equilibrium (UE)	Plasma 1 (P1)	Urine period 1 (U1) ~45 min	Plasma 2 (P2)	Urine period 2 (U2) ~45 min	Plasma 3 (P3)
-5 minutes	Time 0	60 min					

 
Patient to void and collected in U0 container
 
Record exact time
 
	
 
Serum Blood Collection. Two 10ml tubes.
 
iothalamate to be injected SC
 
	
 
All urine to be collected in UE container
 
Record exact time
 
	Collect 0-5 minutes after UE	
 
All urine to be collected in U1 container
 
Record exact time
 
	Collect 0-5 minutes after U1	
 
All urine to be collected in U2 container
 
Record exact time
 
	Collect 0-5 minutes after U2

Subjects be fed a meal and are free to move around during the GFR test. The subject will be instructed to drink sufficient water to ensure a urine flow rate of approximately 3 mL/min to a maximum value of 10 mL/min.
							

Darker shading refers to the two urine collection periods with plasma samples before and after All urine collections to have accurate volume determinations
							

Participants will be fed a meal and are free to move around during the GFR test. The study nurse will assess study subjects following administration of the iothalamate for any adverse events (AE). After the final blood sample, the IV line will be removed if inserted; participants will be observed for approximately 15-30 minutes before they return home.

#### Laboratory analyses

All laboratory tests for samples obtained on the day of GFR measurement will be performed at Mayo Clinic

Rochester or University of Minnesota. Quantification of iothalamate in urine and plasma will be performed using a tandem mass spectrometric method, in the GFR laboratory of [name]. Serum filtration markers will be measured at University of Minnesota. Serum creatinine will be measured using the Roche enzymatic method (Roche-Hitachi P-Module instrument with Roche Creatininase Plus assay, Hoffman-La Roche, Ltd., Basel, Switzerland), traceable to the National Institute of Standards and Technology (NIST) creatinine standard reference material 967 (CV 1.71%). Serum cystatin C will be assayed using the Gentian reagents on the Roche Cobas instrument, which has been shown to be traceable to the International Federation of Clinical Chemistry (IFCC) Working Group for the Standardization of Serum Cystatin C and the Institute for Reference Materials and Measurements (IRMM) certified reference materials. BTP will be measured on the Siemens Dade Behring Nephelometer (CV 5.36%). B2M will be measured on the Roche Modular P (CV 3.2%). Optional blood samples will be aliquoted and stored for future tests including AccuGFR.

## INCLUSION AND EXCLUSION CRITERIA for GFR study

### Inclusion Criteria

1. Consenting participants in RAIN

### Exclusion Criteria

The subject must not meet any of the following:

1. Excluded from RAIN
2. Persons with known allergic reaction to iohexol, iodine, iothalamate or shellfish
3. Inability to cease taking medications that affect creatinine levels (e.g. trimethoprim or trimethoprim-sulfamethoxazole and cimetidine) for two days prior to the study visit
4. Inability to maintain a stable regimen of anti-inflammatory agents and angiotensin converting enzyme inhibitors for one week prior to study visit
5. Current treatment with amiodarone or metformin. Metformin can be stopped the day prior.
6. Acute exacerbation of asthma or chronic obstructive lung disease in the past three months requiring hospitalization or oral steroid therapy
7. Hypercalcemia, defined as a calcium of > 11 g/dL
8. Weight loss >10% over 2 months prior to Day 1 of this study
9. Had a major surgical procedure within 4 weeks prior to mGFR testing

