## 4.2 Exclusion Criteria

Subjects must **not meet any** of the following criteria:

1. Amyloidosis due to mutations of the transthyretin gene or presence of other non-AL amyloidosis
2. Female patients who are lactating, breastfeeding, or pregnant. Men and women of childbearing potential need to use birth control while participating in the study.
3. Patients who have received chemotherapy within 6 months, or SCT within 12 months, for the light-chain producing hematologic disease causing AL amyloidosis, at the time of the first dose of NEOD001 (month 1 day 1)
5. Patients who at initial diagnosis or later met the International Myeloma Working Group (IMWG) definition of active multiple myeloma (Appendix 3)
6. Medically documented cardiac syncope, uncompensated congestive heart failure, myocardial infarction within the previous 6 months, unstable angina pectoris, clinically significant repetitive atrial or ventricular arrhythmias despite antiarrhythmic treatment, or severe orthostatic hypotension or clinically significant uncompensated autonomic insufficiency.
7. Comorbid systemic illnesses or other severe concurrent disease which, in the judgment of the investigator, would make the patient inappropriate for entry into this study or interfere significantly with the proper assessment of safety and toxicity of the prescribed regimens.
8. Ongoing or active infection, known HIV positive, known to be hepatitis B surface antigen-positive or has known or suspected active hepatitis C infection.
9. Psychiatric illness/social situations that would limit compliance with study requirements. This will not be assessed for the study. Patients in active care that limits their ability to come to the center for therapy or patients with family situations that limit their ability to come to the center for therapy will not be eligible because they will not be able to comply with study requirements.

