### Appendix 3 Revised International Myeloma Working Group (IMWG) Diagnostic Criteria for Multiple Myeloma

#### *Definition of Multiple Myeloma*

Clonal bone marrow plasma cells > 10% or biopsy-proven bone or extramedullary plasmacytoma\* and any one or more of the following myeloma defining events:

Myeloma defining events:

- Evidence of end organ damage that can be attributed to the underlying plasma cell proliferative disorder, specifically:
- Hypercalcaemia: serum calcium >0.25 mmol/L (>1 mg/dL) higher than the upper limit of normal (ULN) or >2.75 mmol/L (>11 mg/dL)
- Renal insufficiency: creatinine clearance <40 mL per min† or serum creatinine >177 µmol/L (>2 mg/dL) in the absence of amyloidosis
- Anemia: hemoglobin value of >20 g/L below the lower limit of normal, or a hemoglobin value <100 g/L
- Bone lesions: one or more osteolytic lesions on skeletal radiography, computerized tomography (CT), or PET-CT‡
- Any one or more of the following biomarkers of malignancy:
- Clonal bone marrow plasma cell percentage > 60%
- Involved:uninvolved serum free light chain ratio § > 100
- >1 focal lesions > 5mm in size on magnetic resonance imaging (MRI) studies

PET-CT= F-fluorodeoxyglucose positron emission tomography with computed tomography.

\*Clonality should be established by showing kappa/lambda light-chain restriction on flow cytometry, immunohistochemistry, or immunofluorescence. Bone marrow plasma cell percentage should preferably be estimated from a core biopsy specimen; in case of a disparity between the aspirate and core biopsy, the highest value should be used.

†Measured or estimated by validated equations.

‡If bone marrow has less than 10% clonal plasma cells, more than one bone lesion is required to distinguish from solitary plasmacytoma with minimal marrow involvement.

§These values are based on the serum Freelite assay (The Binding Site Group, Birmingham, UK). The involved free light chain must be > 100 mg/L.

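### Appendix 9 sets the GFR sub-study's hypercalcemia exclusion in g/dL, 1,000 times the mg/dL figure in Appendix 3, so as written it excludes no one

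*Combined protocol and SAP*

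**What the plan says.** Appendix 9 describes the measured-GFR sub-study, in which iothalamate is injected under the skin and its urinary clearance is measured. The only inclusion criterion is "Consenting participants in RAIN". The exclusion list opens with "The subject must not meet any of the following", so meeting any one item is enough to exclude. Item 7 is "Hypercalcemia, defined as a calcium of > 11 g/dL". Table 4 in the same appendix lists the inclusion and exclusion criteria among the screening procedures.

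Appendix 3 (the IMWG myeloma definition) gives the protocol's other numerical definition: "Hypercalcaemia: serum calcium >0.25 mmol/L (>1 mg/dL) higher than the upper limit of normal (ULN) or >2.75 mmol/L (>11 mg/dL". It reaches the main study through one rule, in Section 4.2: "Patients who at initial diagnosis or later met the International Myeloma Working Group (IMWG) definition of active multiple myeloma (Appendix 3".

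**The concern.** The two appendices use the same number, 11, with units that differ by a factor of 1,000. Appendix 9 defines hypercalcemia by that number and unit and leaves no room for investigator judgment, so the unit is part of the rule. Taken literally, a patient with hypercalcemia passes item 7 and is eligible for the clearance test, and an eligibility check built from the text would pass everyone.

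The item matters because it is applied before a procedure for which Appendix 9 itself lists adverse reactions, including very rare renal failure and serious cardiovascular events. The sub-study criteria also decide who contributes to measured GFR at study entry, a secondary endpoint in Section 3.2.2.

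**Working it through.** **Inputs**

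- Appendix 9, exclusion 7: calcium above 11 g/dL.
- Appendix 3: calcium above 2.75 mmol/L, equated to 11 mg/dL; or more than 0.25 mmol/L, equated to 1 mg/dL, above the upper limit of normal.
- Molar mass of calcium: 40.078 g/mol. This is a physical constant and is not given in the documents.

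**Formula:** mg/dL = mmol/L × 40.078 / 10, and 1 g = 1,000 mg.

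**Step 1. Does Appendix 3 agree with itself?**

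- 2.75 × 40.078 / 10 = 11.02 mg/dL, against 11 stated.
- 0.25 × 40.078 / 10 = 1.00 mg/dL, against 1 stated.

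Both pairs reproduce, so the Appendix 3 units are sound.

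**Step 2. Convert the Appendix 9 limit as printed.**

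- 11 g/dL × 1,000 = 11,000 mg/dL.
- 11 g/dL × 10 = 110 g/L.
- 11,000 × 10 / 40.078 = about 2,745 mmol/L.

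The outside constant is not essential. Appendix 3's own pairing implies 11 / 2.75 = 4 mg/dL per mmol/L, which gives 11,000 / 4 = 2,750 mmol/L.

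**Step 3. Compare.**

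| Place | mg/dL | mmol/L |
|---|---|---|
| Appendix 3 | 11 | 2.75 |
| Appendix 9, as printed | 11,000 | about 2,745 |
| Appendix 9, if the unit were mg/dL | 11 | 11 × 10 / 40.078 = 2.74 |

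The ratio is 11,000 / 11 = 1,000 exactly. Blood cannot hold 110 g of calcium per litre, so the printed criterion excludes no one.

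**Step 4. Does another rule catch these patients?**

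- No other section restates or corrects the sub-study limit.
- The main-study criteria (synopsis and Sections 4.1 and 4.2) contain no stand-alone calcium limit.
- Exclusion 1 of the sub-study removes anyone excluded from RAIN. For calcium, that route runs only through the myeloma definition, which also requires clonal marrow plasma cells above 10% or a biopsy-proven plasmacytoma. A participant who is hypercalcemic for another reason is not caught.

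Item 7 is therefore the only rule on calcium itself before the injection, and as printed it has no effect.

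**The case against.** The strongest reply is that nobody would be misled. The item names the condition before it gives the number, and a limit of 110 g/L is so absurd that a clinician would supply the missing letter. On that view the 0% describes the printed string and not likely enrolment. The documents give no prevalence of hypercalcemia and describe no automated calcium check, so the coded-check scenario is a possibility and not a documented process. All of this is fair, and it is why the point is minor. It does not make the text right: a site that reads through the error is applying a limit the protocol does not state.

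A second reply is that the letter may have been lost in text conversion. The abbreviation list under Table 1, for example, prints ECOG without its first letter. That cannot be ruled out from the text alone. But the sentence in Appendix 9 is intact, mg/dL is preserved in Appendices 1 and 3, and a look at the source file would settle it.

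A third is that Appendix 3 is a myeloma definition with a second limb relative to the upper limit of normal. It serves another purpose, and neither appendix cites the other. That is correct. Appendix 3 is a comparator within the document and not the source of the sub-study rule. The impossibility of 11 g/dL does not depend on it.

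Finally, the scope is narrow. Section 3.1 says patients may have these renal function studies, they take one day, and the documents do not say why hypercalcemia is excluded. No effect on the measured-GFR results can be derived from them. That stands too.

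**Conclusion.** The concern holds. The hypercalcemia limit in Appendix 9 is 1,000 times the figure that Appendix 3 gives with the same number, and as written it excludes 0% of patients. The conclusion rests on the printed unit, on standard conversion, and on the absence of any other stand-alone calcium limit in the protocol.

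The consequence is small. The most likely explanation is a slip of g for mg. The primary endpoint, the sample size and the randomized comparison are unaffected, and nothing in the documents shows that a hypercalcemic participant was or would be tested. It is worth correcting because it is an operative eligibility threshold, not because it threatens the trial's conclusions. This finding says that the units conflict; it does not say what calcium limit is clinically appropriate.

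**What to change.** Reconcile the unit in Appendix 9, exclusion 7, with the one Appendix 3 uses for the same number, after confirming the wording in the source file. Check the sub-study eligibility form, and any edit check built from it, for the same error.

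The cost is a one-word correction at the next amendment and a brief check of the form. No design, sample-size or analysis change follows.
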